2.2.3 Randomization

Centre of Excellence VEGA Training and Research Project

Randomization will occur after consent has been obtained and the web-based baseline (Time 1) survey is complete. As indicated in the previous section, randomization will occur five business days before the facilitator-led VEGA session the participant is available to attend is scheduled. Participants will be randomly assigned to one of the two conditions using stratified block randomization, with a block size of 4 (blocking factor of 2), using an internet-based randomization service; <https://www.randomize.net/>. Randomization will be stratified based on sex at birth with two levels to this variable: female and male.

Participants will be informed of their treatment arm status by the RC. The RC will not reveal participant allocations to the RA who will be directly involved in the quantitative data collection. Participants will also be encouraged not to inform the RA of their allocation.

As of March 2023, participants will not be randomized to complete either facilitator-led or self-directed VEGA, all participants will be asked to complete self-directed VEGA.

2.2.4 Education Intervention

Self-Directed VEGA – Experimental Arm uses an approach where participants complete the Violence, Evidence, Guidance, Action Project (VEGA) content online as a self-directed educational activity, at their own pace in a series of modules. Individuals will register to access the VEGA Education Resources site at <https://vegaproject.mcmaster.ca/>. Registration will be free. They will be asked to provide their name and email to be sent the online resources. They will also be asked to agree to terms of use to access this site. Participants will be sent an information sheet that outlines the steps to register and access the VEGA materials online [“CoE_VEGA_SelfDirectedRegistration_V6_03MAR2023.”]. Participants have the option of completing the self-directed VEGA arm in either English or French as the VEGA Educational Resources site offers the content in French and English. The consent form will inform participants this is an option for the self-directed VEGA arm only. The information sheet for registering for self-directed VEGA will also show participants how to access the French version of the VEGA online modules [CoE_VEGA_SelfDirectedRegistration_V6_03MAR2023.”].

Participants will be asked to direct all content-related questions to the RC who will forward them to the VEGA team to see if they can be answered. Participants will be provided the contact information for the VEGA IT Team who will address any technology-related questions they may have while completing the self-directed VEGA program [see “RISE with Veteran Service Providers – Training Program Assignment” in CoE_VEGA_EmailScripts_V8_12MAY2023]. If they haven’t completed them already, participants will receive reminders via email every two days from the RC reminding them to complete the self-directed VEGA online modules [see “RISE with Veteran Service Providers – Online Modules Reminder” in CoE_VEGA_EmailScripts_V8_12MAY2023”].

Participants will be asked to complete the self-directed VEGA at their convenience, within one week of when they are informed they have been asked to complete the self-directed VEGA program. It will take approximately 3 hours for participants to complete all modules.

Facilitator-Led VEGA – Active Control Arm uses a group-based approach where participants complete the Violence, Evidence, Guidance, Action Project (VEGA) content as a virtual or face-to-face workshop (i.e., *facilitator-led VEGA*). In this study, all workshops will be virtual to prevent social gathering during COVID-19. The AC intervention will be facilitated via Zoom technology, by two trained facilitators with between 15 to 20 participants in each workshop (keeping the recommended 10:1 participant-to-facilitator ratio) and will last approximately 3 hours. The workshop approach is delivered by trained facilitators and is standardized via the use of a flexibly structured facilitator's guide.

As of March 2023, no participants will be asked to complete facilitator-led VEGA, as we are removing this arm from the study.

VEGA training takes approximately 3 hours to complete and pedagogical elements for both approaches have been informed by education scholarship. Below is a table outlining the common pedagogical elements in the self-directed and facilitator-led VEGA education interventions (Table 1).

Table 1: Pedagogical Elements of Self-Directed VEGA (i.e., experimental arm) and Facilitated VEGA (active control arm) Educational Approaches

Pedagogical Elements	Self-Directed VEGA (Experimental Arm)	Facilitator-Led VEGA (Active Control Arm)
Didactic Material[45]	Asynchronous reading	Synchronous lecturing
Deliberate practice[46, 47]	Case-Based Animated Simulations	Case-Based Role play
Enabling learning tools [48]	Virtual Patients, Clinical Handbook, Clinical Scripts	Virtual Patients, Clinical Handbook, Clinical Scripts
Test-enhanced learning [43]	Individual multiple-choice questions with response feedback	Group-based polling (i.e., multiple-choice) and feedback.

3.0 Data Collection

3.1.1 Feasibility Statistics

The RC will keep track of the number of providers who: (a) agreed to be screened; (b) are eligible for participation; and (c) enroll. We will also record the number of: (d) emails/phone calls needed to arrange all research assessments; (e) participants who drop out; participants who (f) could not be reached for follow-up; (g) complete the intervention; and (h) partially complete vs. fully complete research assessments for our Primary Objectives. As an indicator of feasibility, we will also record the total time to complete all quantitative assessments.

3.1.2 Quantitative Assessments

A trained research assistant (RA) will gather all data from all participants during three study assessment time points. Quantitative assessments will be hosted on REDCap and will be available online using a web-based link and emailed to participants at three time points: the week before they begin the VEGA training (Time 1), post-education (Time 2), and 3-months after the Time 1 survey is completed (Time 3). Participants will be asked to complete the surveys within one week, from the date they are initially sent, on their own time. Time 1 surveys will be sent

Centre of Excellence VEGA Training and Research Project

after completing the consent form, Time 2 will be sent the day after the online modules are due to be completed (experimental arm), and Time 3 will be sent 3 months after this date, to be completed within two weeks. Each survey will take approximately 30 minutes to complete. A detailed list and description of study measures can be found below. The format of all of surveys, listing all of the questions in each questionnaire can be found in [“CoE_VEGA_QuantitativeSurvey_V3_12MAY2022”]. Due to changes in requirements for continuing education credits, we created an alternative version of the survey [“CoE_VEGA_QuantitativeSurveyB_V3_24MAR2023”] that excludes the measures “Child Maltreatment Knowledge and Skills Questions developed by the VEGA team” and “Satisfaction with VEGA training” because the VEGA team will administer questions required for continuing education credits. As of March 2023, all participants in the study will be administered this version [CoE_VEGA_QuantitativeSurveyB_V3_24MAR2023], we will not be administering the original version [CoE_VEGA_QuantitativeSurvey_V3_12MAY2022]. As a courtesy, participants will also have the option of completing the surveys in either English or French. Before each survey, they will be asked if they would like to complete the current survey in English or French.

3.1.3 Qualitative Interviews

Informed consent procedures for the quantitative strand (see above) will include permission for the research team to approach participants for qualitative data collection. Given that the qualitative data will complement the quantitative strand of data collection, we will use purposive criterion sampling strategies to select a sub-sample of the providers ($n = 30$) to participate in a one-on-one semi-structured interview with the research team via Zoom conducted in English. We will endeavour to stratify recruitment of qualitative participants by sex at birth (~15 male; ~15 female).

Half of the individual semi-structured interviews ($n = 15$) will take place post-intervention completion and half will take place ($n = 15$) will take place 3 months after the intervention has been completed. Interviews will be up to 60-minutes in length. Interviews will be scheduled between an experienced qualitative, education research scholar and the participant at the participant's convenience. Given that members of the research team (Co-PIs and RA) will be involved in the coordination and delivery of VEGA resources and quantitative data collection components, it is essential to have a contract interviewer to conduct the qualitative interviews to support the unbiased collection of data. Interviews will occur by Zoom, using the audio function only (or by phone, if the participant prefers). Interviews will be audio recorded, and will be transcribed verbatim. A semi-structured interview guide of 5-to-7 key questions and probes will guide the interview [see “CoE_VEGA_Qualitative Interview_V6_12MAY2023”]. Field notes completed by the interviewer will document observations, patterns or dialectical positions which may be relevant to analysis.

3.2 Measures

3.2.1 Secondary Outcome Measures

Child Maltreatment Vignette Scale (Pelletier et al., 2014; Pelletier & Knox, 2017). The Child Maltreatment Vignette scale (29, 30) is a psychometrically validated measure of knowledge and skill accuracy related to recognizing and responding to child maltreatment. Respondents will be prompted to review 14 distinct analog vignettes that depict a range of signs

and symptoms of possible CM exposure. Upon completing their review of each vignette, providers will be asked to indicate their responses to two questions, “For any child/youth in this scenario, do you have reason to suspect child maltreatment?” and “Would you report this case to Child Welfare Services?” These changes to the question wording and small changes to the wording of the scenarios were made to align the measure with the Canadian context. Responses will be scored as either correct (‘1’) or incorrect (‘0’) as predetermined, *a priori*, by a panel of CM experts; **a mean “knowledge and skill accuracy” score will be produced for analysis**, with higher scores indicative of greater knowledge and skill accuracy related to CM. They will also be asked their relative confidence in their response on a scale from 50-100%. This will be administered as part of the surveys at **all three timepoints**. In a future RCT, this would be one of the primary outcomes of interest since this is a robust measure of practitioner knowledge and skills related to CM. Time to administer is approximately 15 minutes.

Child Maltreatment Knowledge and Skills Questions (Developed by VEGA Team).

Participants will be asked a series of questions about their knowledge and skills related to recognizing and responding to child maltreatment. These were developed by the VEGA training research team to capture specific aspects of CM knowledge directly addressed in the VEGA intervention and which are outside the scope of the child maltreatment vignette scale. The questions ask about the following topics (and more not mentioned here): parental/family risk factors for family violence, what future outcomes are associated with child maltreatment, other possible signs of child abuse, and principles for good documentation and providing ongoing care to children experiencing maltreatment. A full list of the questions can be found in Section 2.4 of the quantitative survey (see Section 2.4 of CoE_VEGA_QuantitativeSurvey_V3_04MAY2022). Including this measure in our study will allow us to make cross sample comparisons.

The Physician Readiness to Manage Intimate Partner Violence Survey (Short et al., 2006; Connor et al., 2011).

The Physician Readiness to Manage Intimate Partner Violence Survey (PREMIS) is a 67-item self-report tool that was developed to assess physician management of intimate partner violence across 10 subscales (31, 32). Survey questions are grouped into four major sections (1) background (four scales concerning previous IPV training, perceived IPV knowledge and preparation), (2) actual knowledge, (3) IPV attitudes and beliefs, and (4) practice issues (a 13-item scale of self-reported behaviors concerning individual and office IPV practices and policies).

- a. **PREMIS Section III: IPV Knowledge.** The IPV knowledge section, consisting of multiple answer, multiple choice, and true-false questions will be used to measure IPV knowledge and skills. An IPV “knowledge score” will be computed following previous scoring guidelines (Short et al., 2006). In a future RCT, this would be a primary outcome of interest to measure practitioner knowledge and skills related to IPV. **This will be administered as part of the surveys at all three timepoints.** Time to administer is approximately 10 minutes.

- b. PREMIS: Adapted Preparedness Subscale.** The preparedness subscale of PREMIS asks respondents to indicate the extent to which they feel prepared to address various aspects of IPV recognition and response when working with their clients across 10 items; these aspects include the conduct of safety assessments, asking appropriate questions about IPV, responding to IPV disclosures, among others. Response options are on a 7-item Likert type scale ranging from “Not prepared” (1) to “Quite Well Prepared” (7) and items are averaged to generate a mean score for practitioner preparedness, with higher scores indicative of generally greater preparedness to recognize and respond to IPV.

For the purposes of this study, an adapted version of the preparedness subscale was used to assess preparedness to recognize and respond to IPV. The last item, “Fulfill state reporting requirements for (a) IPV, (b) child abuse, and (c) elder abuse” was dropped because other questionnaires in this survey address providers’ self-reported ability to fulfill these requirements, for a total of 9 items. Total scores for preparedness to respond to IPV will be calculated by summing the responses selected for all 9 items and will range from 9 to 63.

An adapted version of the preparedness subscale was administered to assess provider’s preparedness to recognize and respond to CM. All items were changed to be related to CM instead of IPV (e.g., “ask appropriate questions about IPV” was changed to “ask appropriate questions about CM”). Several items were dropped from the subscale as they are not relevant in the case of CM: “Help an IPV victim assess whether their life is in danger,” “Conduct a safety assessment related to IPV”, “Help an IPV victim create a safety plan,” for a total of 6 items. Total scores for preparedness to respond to IPV will be calculated by summing the responses selected for all 6 items and will range from 6 to 42.

These two versions of the preparedness subscale will be administered at Time 1, Time 2, Time 3. Time to administer is approximately 2 minutes, a total of 4 minutes to administer both the IPV and CM versions.

- c. PREMIS: Opinions.** The Opinions section of the PREMIS asks respondents to indicate their level of agreement/disagreement with various statements about care of those with IPV across 32 items. Response options are on a 7-item Likert type scale ranging from (1) Strongly Disagree to (7) Strongly Agree. We will use an adapted version of this scale which dropped items related to their compliance with legal requirements for IPV. This adapted version will be used to measure provider attitudes and beliefs about IPV and care of those with IPV in five subscales: (1) preparation, (2) workplace issues, (3) self-efficacy, (4) alcohol/drugs, and (5) victim understanding. We will follow previous methods to calculate these subscales by averaging the responses to items that make up the subscale (Short et al., 2006). **The opinions section of the PREMIS will be administered at Time 1 and Time 3, with the exception of the self-efficacy questions which will be administered in a**

separate section at Time 2 as well. It will take approximately 10 minutes to complete.

- d. PREMIS: Self-Efficacy Subscale.** The self-efficacy subscale of the PREMIS comprises three questions from the Opinions section of the PREMIS: “I ask all new patients about abuse in their relationships,” “I feel comfortable discussing IPV with my patients,” and “I am able to gather the necessary information to identify IPV as the underlying cause of patient illnesses (e.g. depression, migraines).” **The self-efficacy score is calculated by averaging the responses of these three items.** This will be a primary outcome of interest in a future RCT as a measure of provider’s self-efficacy to recognize and respond to IPV. **The three items comprising this subscale will be administered at Time 1, Time 2, and Time 3,** and will take approximately 1 minute to administer.

Mandatory Reporting Self-Efficacy Scale (Ayling, 2019). The Mandatory Reporting Self-Efficacy Scale (MRSES) is a 7-item self-report measure that asks respondents to indicate the extent to which they perceive their ability to implement a series of behaviours related to mandatory reporting of CM (33). Informed by Bandura’s self-efficacy theory and recommendations for self-efficacy scales (34), response options are anchored on a scale from 0 to 100 with statements at 0, 50, and 100 indicating: “cannot do at all (0)”; moderately can do (50)”; and “highly certain can do (100).” A total score is generated by summing items across the scale for each participant, with higher scores indicative of greater self-efficacy related to recognizing and reporting suspected CM. We anticipate that this measure will be a key mediator of interest in a future definitive RCT given that across provincial and territorial jurisdictions in Canada (including Ontario), a suspicion of CM meets the threshold for a report to child protection authorities (35,36). This will be administered as part of the surveys at all three timepoints. Time to administer is approximately 5 minutes.

Brief Individual Readiness for Change Scale (Goldman, 2009). The Brief Individual Readiness for Change (BIRCS) scale is a 5-item readiness for change tool (39). The scale’s purpose is to screen for practitioners’ readiness for change, in other words their receptivity to learning and applying new evidence-based research practices. For the purpose of this study, the items were adapted to assess provider’s readiness to recognize and respond to all forms of (a) IPV and (b) CM in their practice. Response options range from ‘0’ Strongly Disagree to ‘4’ Strongly Agree. Two items were added, “I believe recognizing and responding to [IPV/CM] in my practice improves outcomes for my clients,” and “I am motivated to learn about [IPV/CM]” to capture other aspects of providers’ readiness to learn about IPV and CM and their beliefs about how this will impact their practice. Total and average scores will be calculated by summing or averaging the item responses for both the original scale items and with the added two items. These two versions of the scale will take approximately 1 minute each to complete and will be administered at Time 1 and Time 2.

3.2.2 Other Measures

Demographics

Sociodemographic characteristics will be collected for all participants who are screened for the study, whether they are ineligible or eligible. These will include their age, province of practice, highest level of education attainment, their major discipline, their sex at birth and their self-identified gender. We will also collect some characteristics about the current organization or practice they work for, specifically what populations among military and/or RCMP veterans and their families they serve and if consent is required by the veteran for the participant to provide services to a family member. A full list of all demographic questions can be found in “Appendix A: Screening and Demographics Call REDCap Form” of “CoE_VEGA_ScreeningCallScript_V7_03APR2023.”

Previous Training in Intimate Partner Violence and Child Maltreatment

At Time 1 only, participants will be asked questions to gauge their previous education or training in IPV and CM. Participants will be given a definition of IPV and CM and asked in what subject areas of IPV and CM they have received education and training in, and which of these environments (up to three) have been the most helpful.

Thoughts and Beliefs about Recognizing and Responding to IPV and CM in Professional Roles

Participants will be asked to rate their agreement with four statements about how much they believe (1) recognizing IPV (2) recognizing CM (3) responding to IPV and (4) responding to CM is a part of their professional role. We are recruiting a wide variety of HHSPs that we anticipate may vary in their self-perceptions of how relevant recognizing and responding to IPV and CM is in their professional roles. This will be administered at Time 1 and Time 2 and will take approximately 1 minute to complete.

Satisfaction with VEGA Training

At Time 2, participants will complete a series of multiple choice and short-answer questions asking what they thought about the VEGA training. These questions will apply to all participants whether they completed self-directed or facilitator-led VEGA. Questions will include whether they believe the intended learning outcomes were achieved, what they thought of the instructional materials and educational scenarios, and how they would rate the usefulness of VEGA.

4.0 Statistical Analyses

4.1 Quantitative Analyses

4.1.1 Sociodemographic Characteristics: Descriptive statistics (means, standard deviations, relevant quantiles, and proportions) will be used to report the sample of HHSP's sociodemographic characteristics.

4.1.2 Primary Outcomes: Descriptive statistics (totals, means, standard deviations) will be used to compare primary outcomes to a priori thresholds for acceptability and feasibility outlined in section 2.1.2 Primary Aims.

4.1.3 Secondary Outcomes: Our secondary outcomes will be analyzed via generating bivariate correlations and regression coefficients for variables we hypothesize to be mediators, moderators, and outcomes for a definitive trial.

4.1.4 Missing Data: We will use a force-choiced framework in REDCap in to reduce the possibility of missing data..

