Primary outcomes of feasibility will be obtained by the RC tracking the recruitment and administration of the VEGA resources. The perceived acceptability and impact of the approaches will be determined by qualitative interviews conducted in a sub-sample of participants. The evaluation of secondary outcomes will be powered to detect moderate self-reported improvements in IPV and CM knowledge and skills, as well as preparedness and self-efficacy related to recognizing and responding to IPV and CM. These secondary outcomes will be obtained via self-report surveys administered at baseline (Time 1), post-education (Time 2), and at 3-month follow-up time points (Time 3).

2.1.2 Mixed Method Research Design.

We will use the embedded-experiment (QUAN(qual)) mixed method research design (26, 27). A strand of quantitative data collection will provide important acceptability and feasibility metrics related to enrollment, retention, attrition, data completeness, as well as exploratory estimates of education effect for the VEGA resources. The qualitative strand of data collection will generate important contextual information regarding the tenability of an RCT, the perceived value and impact of the VEGA resources and examine the *why* of acceptability and feasibility, as well as educational impact (or not) from the perspective of veteran-service providers.

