2.1.3 Primary and Secondary Aims

Primary Aims: To determine the feasibility and acceptability of an RCT comparing two VEGA educational approaches, the self-directed vs facilitator-led VEGA, in HHSPs who serve veterans and their families. To determine the feasibility of the RCT we will use four outcomes: (i) the number of HHSPs who meet eligibility criteria and (ii) who agree to be randomized to either self-directed or facilitator-led VEGA education approaches, both overall and per week of recruitment, (iii) the proportion of HHSPs who complete each arm, with completion consisting of the review of all module content and the animated simulations in the case of self-directed VEGA and full attendance of the virtual workshop in the case of facilitator-led VEGA and (iv) the feasibility of collecting trial outcome data at Time 1, Time 2, and Time 3. The acceptability of the facilitator-led and self-directed educational approaches as well as their value and impact will be determined via the coding of qualitative interview data from a sub-sample of participants.

Our aims are that (i) we will recruit, on average, 5 providers per week and achieve our sample aims of 80 participants within 16 weeks, (ii) the proportion of providers who contact the research team about participation and who consent to randomization will be 70% or greater, (iii) the proportion of providers who are randomized and complete their assigned intervention will be 70% or greater for each arm and (iv) the proportion of missing data for each time-point will be less than 20%.

Centre of Excellence VEGA Training and Research Project

As of March 2023, we will revise primary outcomes (ii) and (iii) to (ii) the number of HHSPs who consent to participate in the study and complete self-directed VEGA, both overall and per week of recruitment, (iii) the proportion of HHSPs who complete self-directed VEGA, with completion consisting of the review of all module content and the animated simulations in the case of self-directed VEGA. Our aims are (ii) the proportion of providers who contact the research team about participation and who consent to participate will be 70% or greater and (iii) the proportion of providers who complete self-directed VEGA will be 70% or greater.

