4.2 Sample Size

We will recruit a voluntary sample of 80 HHSPs that will be randomized to either the experimental or AC arm. We have selected this sample size given previous work which indicates that 40 HSSPs per arm would provide 80% power to detect a moderate (0.5 SD – to – 0.6 SD) effect size, which is indicative of a clinically significant outcome (40).

As of March 2023, we are now focusing on achieving sample size aims for one of the two arms of the study and no longer going to evaluate the facilitator-led VEGA. Our primary aim will be achieved by conducting a one-arm pilot trial of 40 veteran-serving HHSPs where participants will complete self-directed VEGA. In following this algorithm, our team will be able to consider the needed recruitment and retention rates to successfully implement a definitive education trial.

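### Primary criterion (iv) on missing data has no stated unit or denominator, and section 4.1.4 covers skipped items but not unreturned or abandoned surveys

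*Combined protocol and SAP*

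**What the plan says.** Section 2.1.3 names the fourth primary outcome as "the feasibility of collecting trial outcome data at Time 1, Time 2, and Time 3". Its target is that "the proportion of missing data for each time-point will be less than 20" per cent. No numerator, denominator or unit is given, and the March 2023 revision changes criteria (ii) and (iii) but leaves (iv) as it was.

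Section 4.1.4 consists of one sentence: "We will use a force-choiced framework in REDCap in to reduce the possibility of missing data". It does not mention unreturned surveys, surveys left midway, loss before Time 2 or Time 3, or the analysis set.

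Section 3.1.1 does plan some relevant counts: "participants who drop out; participants who (f) could not be reached for follow-up", and "partially complete vs. fully complete research assessments for our Primary Objectives". Section 2.1.2 promises "metrics related to enrollment, retention, attrition, data completeness". None of these counts has a threshold or a stated link to (iv).

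For the secondary outcomes, section 2.1.3 hypothesises increases from Time 1 to Time 2 and from Time 1 to Time 3. Section 4.1.3 offers correlations and regression coefficients, with no rule for providers whose follow-up is incomplete. Section 4.2 sets the current size: "conducting a one-arm pilot trial of 40 veteran-serving HHSPs where participants will complete self-directed VEGA".

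**The concern.** A forced response stops a provider from skipping an item in a survey that is then submitted. It does nothing about a survey that is never opened or is closed halfway, and in an emailed follow-up these are the losses that remain.

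Criteria (ii) and (iii) are worded as proportions of providers; (iv) is a proportion of data. Section 2.1.2 lists retention and attrition separately from completeness, and 4.1.4 treats missing data only at item level. A reader could therefore fairly compute (iv) within returned surveys. Another could fairly compute it over everyone enrolled. The two can give opposite results on one of four primary criteria, and a denominator chosen after the data are seen could choose the verdict.

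No other criterion would catch the loss. Criterion (i) is recruitment, (ii) is consent and (iii) is completion of the training; a provider can finish the modules and never return Time 3. Section 4.2 says the pilot should inform retention rates for a definitive trial, so a threshold on survey return is one it needs.

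The same gap reaches the secondary outcomes. Without a rule for incomplete follow-up, estimates of change may rest only on those who returned both surveys.

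**Working it through.** **Inputs.** Threshold: below 20% at each time point (2.1.3). Sample: 40 in the current one-arm design, 80 in the two-arm design (4.2). The documents give no expected rate of non-return, so the numbers of unreturned surveys below are assumptions, shown over a range. The 20% is a chosen threshold without a derivation, so there is no figure to reproduce.

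**Two readings.** Let N be the number enrolled and u the number of surveys not returned at a time point.
- Returned-surveys reading: missing items ÷ items due in returned surveys. With forced response and no abandoned surveys this is 0 ÷ (items in N − u surveys) = 0%.
- All-enrolled reading: u ÷ N.

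**Result at N = 40.**

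| u | Returned-surveys reading | All-enrolled reading |
|---|---|---|
| 7 | 0%, pass | 7/40 = 17.5%, pass |
| 8 | 0%, pass | 8/40 = 20.0%, fail |
| 10 | 0%, pass | 10/40 = 25.0%, fail |
| 20 | 0%, pass | 20/40 = 50.0%, fail |
| 30 | 0%, pass | 30/40 = 75.0%, fail |

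Because the criterion is strictly below 20%, the largest passing count on the all-enrolled reading is 7 at N = 40. At N = 80 it is 15 (15/80 = 18.75%), and 16 (20.0%) fails.

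**Abandoned surveys.** Assume 10 of 40 are not returned and 5 of the 30 opened are abandoned halfway.
- Items missing among opened surveys: 0.5 × 5 ÷ 30 = 8.3%, pass.
- Items missing among all enrolled: (10 + 0.5 × 5) ÷ 40 = 31.3%, fail.
- Providers without a fully completed survey: (10 + 5) ÷ 40 = 37.5%, fail.

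So item-level missingness need not be zero, yet the readings still disagree.

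**Possible effect on a change estimate (illustration only).** Assume returners change by 0.5 SD. If a fraction f does not return and changes by d, the mean over all enrolled is (1 − f) × 0.5 + f × d.
- f = 12/40 = 0.30, d = 0: 0.7 × 0.5 = 0.35 SD.
- f = 10/40 = 0.25, d = 0: 0.75 × 0.5 = 0.375 SD.
- d = 0.5: 0.50 SD whatever f is.

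At 30% non-return, an estimate from returners alone is 0.50 SD, while the all-enrolled mean runs from 0.35 to 0.50 SD as d goes from 0 to 0.5. None of these inputs comes from the documents.

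**The case against.** A reader might infer something stronger: that forced choice fixes item-level missingness at zero, that (iv) can therefore be met whatever the survey return, and that non-returners will be dropped without a report. The documents do not support this.

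- Section 4.1.4 claims only a reduced possibility of missing data, and 3.1.1 expects to record "partially complete vs. fully complete research assessments".
- Restricting (iv) to returned surveys is a qualifier that section 2.1.3 does not contain. The outcome concerns whether data can be collected at three time points, and an uncollected survey is a failure of exactly that. The all-enrolled reading fits at least as well, and under it (iv) can fail.
- Dropouts and unreached participants are to be counted, so heavy loss would be visible. No passage prescribes a completer-only analysis or unreported exclusions.

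It can also be said that the SD contrast follows wholly from its assumptions, that a mixed model is a lot to ask of a 40-person pilot whose effect estimates are exploratory, and that such a model assumes data missing at random, so it would not by itself correct loss that depends on having failed to improve.

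These points narrow the finding but leave its core. The plan never says which reading of (iv) applies, its counts of survey loss have no threshold, and it gives no rule for incomplete follow-up. The missing-at-random point is a reason to add a sensitivity analysis alongside the model.

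**Conclusion.** The point stands as an undefined primary criterion together with an incomplete missing-data plan. It does not show that (iv) cannot fail. At N = 40, 10 unreturned surveys give 0% or 25% depending only on the denominator. The readings agree on a pass up to 7 unreturned surveys and part at 8, provided no opened survey is abandoned. This rests on the target of 40 being reached and on an assumed number of non-returners. The SD figures show how large a completer-only distortion could be under one assumption and are not a prediction. The gap should be closed before results are seen; it does not undermine the design.

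**What to change.** **Section 2.1.3.** Define (iv) at each time point as the number of consented providers without a fully completed survey divided by all consented providers. Count unreturned and partial surveys as missing. With 40 consented, 7 missing passes and 8 fails. Report late but complete surveys separately and do not count them as missing.

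**Section 3.1.2.** Reconcile the Time 3 details. The section gives a one-week window for the surveys in general but two weeks for Time 3, and it anchors Time 3 once to completion of Time 1 and once to the date Time 2 is sent. Until this is settled, a late survey cannot be identified.

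**Sections 4.1.3 and 4.1.4.** Estimate the Time 1–2 and Time 1–3 changes with a repeated-measures mixed model that uses every available survey. This addresses the stated hypotheses directly, which correlations and regression coefficients do not. Add one sensitivity analysis that assumes no change for non-returners, because the model alone assumes data missing at random. State the number of providers contributing at each time point.

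**Cost.** Wording changes and slightly more analysis. Section 3.1.1 already plans most of the counts, so no new data collection is needed. The real price is that (iv) becomes harder to meet than on the returned-surveys reading.
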